5.2. Sub-Study Breaking the Blind

This sub-study will be subject-, investigator- and Sponsor blinded.

In regards to each sub-study drug:

- Tofacitinib 5 mg BID will be open label;
- The assignment of MTX/MTX placebo will be subject-, investigator-, and Sponsor-blinded.

At the initiation of the sub-study the investigator site will be instructed on the method for breaking the blind. The method will be an electronic process using the IRT system. Blinding codes should be broken only in exceptional circumstances when knowledge of the actual treatment code is absolutely essential for further management of the subject. Investigators are encouraged to discuss with a member of the study team if they believe that unblinding is necessary. When the blinding code is broken, the reason must be fully documented on the case report form (CRF).

5.3. Sub-Study Drug Supplies

The Sponsor will provide tofacitinib 5 mg tablets in a bottle that will be labeled as appropriately for this sub-study. MTX 2.5 mg capsules and matching placebo will also be provided by the Sponsor. Study medication will be taken according to the instructions provided to the subject. The specific subject instructions will also direct the subject to bring the study medication bottle(s) to the clinic on study visit days. Dose increases for both tofacitinib and blinded MTX are not permitted during this sub-study. Temporary withdrawals of any study drug or MTX dose reductions due to safety concerns may occur between scheduled study visits and must be clearly documented on the subject's chart and verified for start date and dose when the subject returns for their next scheduled visit.

5.3.1. Sub-Study Preparation and Dispensing

Tofacitinib, blinded MTX and the corresponding MTX placebo will be dispensed in bottles. At each dispensing visit, subjects will receive a sufficient quantity of all study drugs to last

until their next scheduled dispensing visit. The subject should be instructed to maintain the product in the container provided throughout the course of dosing and return the containers at the next study visit. At all study visits, subjects' returned containers will be assessed for accountability and the amount of study drug returned will be recorded.

5.4. Sub-Study Administration

All investigational products will be self-administered by the subject as specified in the dosing card. Tofacitinib should be administered orally, twice daily, approximately 12 hours apart, once in the morning and once in the evening. During the sub-study all subjects will receive a dose of 5 mg BID taking 1 tablet in the morning and 1 tablet in the evening. If a tofacitinib dose is missed and the interval to the next scheduled dose is less than 6 hours, the missed dose of tofacitinib should not be administered.

At the time of enrollment (eg, the Combined A3921092 Sub-study Switch/Baseline visit), subjects must discontinue the use of their personal (commercial) supply of MTX. MTX or its matching placebo will be provided by the Sponsor and must be administered orally once a week (the same day of the week) in a predetermined dose that may range from 7.5 mg/week to 20 mg/week. Subjects will receive the corresponding number of MTX or matching placebo 2.5 mg capsules to complete their individual preselected dose of oral MTX (Sub-Study [Table 3](#)). Subjects should be instructed to document any missed doses.

Sub-Study Table 3

Assigned Dose of MTX	Corresponding number of MTX 2.5 mg capsules or matching placebo
7.5 mg/week	3 capsules
10 mg/week	4 capsules
12.5 mg/week	5 capsules
15 mg/week	6 capsules
17.5 mg/week	7 capsules
20 mg/week	8 capsules

Subjects who are randomized to tofacitinib 5 mg BID + MTX placebo will experience a full withdrawal of MTX (eg, no tapering) at the time of randomization.

Study medications may be administered with or without food, with exception of the day of the study visits that require fasting.

Medication errors may result in the sub-study from the administration or consumption of the wrong product, by the wrong subject, at the wrong time, or at the wrong dose. Such medication errors occurring to a study participant are to be captured on the adverse event page of the CRF and on the SAE form when appropriate. In the event of a dosing error, the sponsor should be notified immediately. Whether or not the medication error is accompanied by an AE, as determined by the investigator, it is captured on an adverse event (AE) CRF

page as well as any AEs associated with the medication error (refer to [Section 8](#) of main LTE protocol).

5.5. Sub-Study Compliance

Subject compliance with dosing administration for both tofacitinib and MTX/placebo will be verified by accounting of returned containers and trial medication at each visit.

Compliance for the tofacitinib tablets and MTX/placebo capsules will be monitored by the accounting of unused medication and will be documented. Subjects who demonstrate <80% compliance to either study drug should be counseled by the investigator or designee and ensure steps are taken to improve compliance. Subjects who are <80% compliant with dosage regimen for any of the 2 study medications, for two consecutive visit periods should be withdrawn from the study.

If the subject is over-compliant with either study drug (intentional or accidental) the investigator or designee is to counsel the subject and ensure correct understanding of the study drug dosing regimen. The investigator should contact the Pfizer Study Clinician promptly with any over-compliance (>120% in a visit period) that may potentially impact the safe use of study drug or that may result in a serious adverse event.

5.6. Sub-Study Drug Storage

The investigator, or an approved representative (eg, pharmacist), will ensure that all investigational product, including any comparative agents and/or marketed products are stored in a secured area with controlled access under recommended storage conditions and in accordance with applicable regulatory requirements.

Both investigational products should be stored in its original container and in accordance with the drug label. See the drug label for storage conditions of the product.

Storage conditions stated in the single reference safety document (SRSD), tofacitinib IB and SPC for methotrexate), will be superseded by the storage conditions stated in the labeling.

Site systems must be capable of measuring and documenting (for example, via a log), at a minimum, daily minimum and maximum temperatures for all site storage locations (as applicable, including frozen, refrigerated and/or room temperature products). This should be captured from the time of investigational product receipt throughout the study. Even for continuous monitoring systems, a log or site procedure which ensures active daily evaluation for excursions should be available. The operation of the temperature monitoring device and storage unit (for example, refrigerator), as applicable, should be regularly inspected to ensure it is maintained in working order.

Any excursions from the product label storage conditions should be reported upon discovery. The site should actively pursue options for returning the product to labeled storage conditions, as soon as possible. Deviations from the storage requirements, including any actions taken, must be documented and reported to the sponsor.

Once an excursion is identified, the investigational product must be quarantined and not used until the sponsor provides documentation of permission to use the investigational product. It will not be considered a protocol deviation if Pfizer approves the use of the investigational product after the temperature excursion. Use of the investigational product prior to Pfizer approval will be considered a protocol deviation.

Specific details regarding information the site should report for each excursion will be provided to the site.

Site staff will instruct subjects on the storage requirements for take home medications.

5.7. Sub-Study Drug Accountability

The investigator's site must maintain adequate records documenting the receipt, use, loss or other disposition of the investigational product supplies. At the Switch/Baseline visit of the sub-study, all investigational product from the main A3921092 LTE study will be collected for accountability under the main protocol. New tofacitinib supplies will be dispensed under the sub-study.

To ensure adequate records, all investigational product supplies will be accounted for in the drug accountability inventory forms as instructed by Pfizer and will be monitored by the accounting of unused study drug returned by the subjects. All study drug bottles must be returned to the investigator by the subject and the investigator will return the bottles to Pfizer. At the end of the clinical study, all drug supplies unallocated or unused by the subjects must be returned to Pfizer or its appointed agent, or destroyed in an approved manner unless otherwise authorized by Pfizer. In either case, the forms must identify the study drug, including batch or code numbers, and account for its disposition on a subject-by-subject basis, including specific dates and quantities. The forms must be signed by the individual who dispensed the drug.

5.7.1. Destruction of Investigational Product Supplies

Process for destruction will be as noted in [Section 5.5.1](#) of the LTE protocol.

5.8. Concomitant Treatment(s)

It is important to be aware of, and document, all concomitant treatments including: prescription, non-prescription (ie, over-the-counter) and herbal medications.

A subject who is receiving an allowed concomitant medication for any reason must be on a locally-approved medication and dose that is considered standard-of-care for the treated indication, and this must be documented in the case report form. Subjects are not allowed to receive any other investigational drug during the study.

It is recommended that subjects avoid changing non-prohibited prescription or non-prescription drugs, vitamins, and dietary supplements within 7 days or 5 half-lives

(whichever is longer) prior to the first dose of study medication and prior to study visits unless otherwise noted below, throughout the study.

Treatments that are taken before the first dose of study drug will be documented as prior treatments. Treatments taken after the first dose of study drug has been administered will be documented as concomitant treatments. All concomitant treatments taken during the study must be recorded in the study records with indication (as appropriate), daily dose and start and stop dates of administration. Subjects will be queried about concomitant treatments at each study visit.

Minimum guidelines for folate supplementation during study: All subjects must receive folate supplementation according to local methotrexate label guidelines and standard of care. A minimum of 5 mg weekly based on folic acid should be given unless local guidelines or standard of care state otherwise.

5.8.1. Stable Background Pain or Other Arthritis Therapy

Adjustments for safety reasons may be done at any time, but if this leads to changes in excess of those allowed, the investigator must receive approval from the Pfizer Study Clinician to allow the subject to continue in the trial.

For subjects receiving background NSAID/COX-2 inhibitors, dose adjustments are not permitted in the first 6 months of the sub-study unless there is a safety concern. Switching to other NSAIDs/COX-2 inhibitors is not allowed during the sub-study. Oral corticosteroid dose should not exceed 10 mg prednisone or its equivalent daily. Daily dosage of corticosteroids must not be modified during the sub-study, except if adjustment is needed to protect a subject's safety.

The total daily dose of acetaminophen may not exceed 2.6 grams per day, and the total daily dose of opioid may not exceed the potency equivalent of 30 mg of orally-administered morphine (See [Appendix 5](#), [Appendix 6](#)).

Daily dosage of opioids and acetaminophen/paracetamol must not be modified in the first 6 months of the sub-study, except if adjustment is needed to protect a subject's safety.

5.8.2. Other Medications

Prohibited drugs and dietary supplements must be discontinued according to protocol guidelines: a list of prohibited drugs with specific discontinuation recommendations is listed in [Appendix 3](#). Herbals with pharmaceutical properties are allowed only if there is acceptable evidence of no CYP3A inhibition or induction. Otherwise, herbals with pharmaceutical properties must be discontinued for at least 4 weeks prior to first dose of study drug, unless there is sufficient data available regarding the duration of an herbal medication's pharmacokinetic and pharmacodynamic effects to allow a shorter washout to be specified (eg, 5 half-lives). All concomitant treatment taken during the study must be recorded with indication (as required), daily dose, and start and stop dates of administration.

5.9. Rescue Therapy

The only medications that are allowed for rescue are listed in [Appendix 6](#). Subjects who require rescue medication for more than 10 consecutive days should be discontinued from the study. There is no limit to the total duration of nonconsecutive use of rescue medications. In addition, subjects must not be dosed with rescue medication during the 24 hours prior to a study visit except if adjustment is needed because subject is experiencing intolerable pain.

Baseline stable use of acetaminophen/paracetamol or opioids should NOT be discontinued in advance of study visits.

5.9.1. Dosage Reduction and Withholding

All subjects will receive open-label tofacitinib 5 mg BID and MTX or matching placebo upon entry into the sub-study. Dosage of both tofacitinib and MTX (predetermined dose as described in Sub-Study [Section 5.1](#)) must remain stable for the duration of the sub-study.

If the investigator deems it necessary to withhold any of the study medications to treat a non-serious infection or other medical condition, temporary withholding is permitted for up to 5 days of tofacitinib and 1 weekly dose of MTX. If the study drug administration is interrupted for more than 5 days or 1 weekly dose of MTX due to a medical reason, the investigator must contact the Pfizer study clinician for approval.

Temporary withholding of study medication, as described above, is permitted once during the study without obtaining prior approval from Pfizer Study clinician. Any additional request(s) for temporary withholding of study drug require(s) documented approval by the Pfizer Study Clinician.

Dosage of tofacitinib and/or MTX may be temporarily discontinued for up to 14 consecutive days or 2 weekly doses, for severe cytopenias, for infections which meet criteria for serious infections (ie, those requiring parenteral antimicrobial therapy or hospitalization), for surgical procedures or other moderately severe AEs.

Treatment with tofacitinib will be discontinued and the subject withdrawn from this study due to safety issues as defined in [Appendix 4.3](#).

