5.8. Dosage Reduction and Withholding

All subjects will receive tofacitinib 5 mg BID upon entry into A3921092. Dosage of tofacitinib may be increased to 10 mg BID only at scheduled study visits to provide greater control of the subject's PsA, if the investigator feels the subject would benefit and the subject is not experiencing any tofacitinib-related adverse events, including abnormalities in laboratory parameters that are judged to be related to tofacitinib.

For those subjects whose tofacitinib dose has been increased to 10 mg:

- Dosage of tofacitinib may be reduced back to 5 mg BID for mild to moderate cytopenias, other mild to moderate AEs, or any other safety-related issues, either temporarily or for the duration of the study.
- Definitions of mild to moderate cytopenias are as follows:
 - Mild to moderate neutropenia: 1000-1500 neutrophils/mm³, confirmed;
 - Mild to moderate anemia: a decrease of hemoglobin from 1.0-2.0 g/dL from baseline, inclusive, provided the hemoglobin remains >8.0 g/dL;
 - Mild to moderate thrombocytopenia: 75,000-100,000 platelets/mm³.

For all subjects:

- Dosage of tofacitinib may be temporarily discontinued for up to 28 consecutive days, for more severe cytopenias, for infections which do not meet criteria for serious infections (ie, those requiring parenteral antimicrobial therapy or hospitalization), for surgical procedures or other moderately severe AEs.
- Treatment with tofacitinib will be discontinued and the subject withdrawn from this study for toxicities as defined in [Appendix 4](#).

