8.6.1. Serious Infections

A serious infection is any infection that requires hospitalization for treatment or requires parenteral antimicrobial therapy or meets other criteria that require it to be classified as a serious adverse event. A subject who experiences a serious infection should be discontinued from the study and the serious adverse event should be listed as the reason for discontinuation in the Case Report Form. Appropriate laboratory investigations, including but not limited to cultures should be performed to establish the etiology of any serious infection. All adverse events, including serious adverse events, should be reported as described in [Section 8](#) on Adverse Event Reporting.

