Appendix 4.2. Guidelines for Dose Adjustments of Tofacitinib

The maximum tofacitinib dose allowed is 10 mg BID. All subjects will receive tofacitinib 5 mg BID upon entry into study. Tofacitinib dose may be increased from 5 mg BID to 10 mg BID based upon investigator discretion and should be modified during the study in the following manner:

- Subjects taking tofacitinib 5 mg BID may have their dose increased to 10 mg BID if the investigator feels that the subject's PsA symptoms are not adequately controlled and the subject is not experiencing any tofacitinib-related adverse events, including abnormalities in laboratory parameters that are judged to be related to tofacitinib.
- Dose increases may only occur at scheduled study visits.

Other dosage adjustments that may occur at any time may include:

- Subjects receiving tofacitinib 10 mg BID may reduce dose to 5 mg BID in response to mild to moderate AEs at the discretion of the investigator, either temporarily or for the duration of the study. If the dose has already been decreased to 5 mg BID, the dose may be temporarily discontinued for up to 28 days.
- Subjects receiving tofacitinib 10 mg BID may reduce dose to 5 mg BID either temporarily or for the duration of the study, after laboratory abnormalities specified in [Appendix 4.1](#) are repeated and confirmed. If the dose has already been decreased to 5 mg BID, the dose may be temporarily discontinued for up to 28 days.
- Dosage of tofacitinib (5 mg or 10 mg BID) may be temporarily discontinued for up to 28 consecutive days, for laboratory abnormalities, for infections which do not meet criteria for serious infections (those requiring parenteral antimicrobial therapy or hospitalization), for surgical procedures or other moderately severe AEs. If treatment must be discontinued for more than 28 days, the subject should be withdrawn from the study.
- If a subject is temporarily discontinued from study drug for up to 28 days due to laboratory abnormalities, safety labs need to be repeated prior to resumption of treatment.
- If a subject taking tofacitinib 10 mg BID is temporarily discontinued from study drug for up to 28 days due to laboratory abnormalities, mild to moderate AEs or for infections that do not meet criteria for serious infections (those requiring parenteral antimicrobial therapy or hospitalization), their study drug should be restarted at 5 mg BID.

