Appendix 4.3. Discontinuation Criteria

Study drug will be discontinued and the subject withdrawn from the study for:

- Requirement of rescue medication for more than 10 consecutive days.
- Serious infections, defined as any infection (viral, bacterial, and fungal) requiring parenteral antimicrobial therapy or hospitalization for treatment, or meeting other criteria that require the infection to be classified as a serious adverse event (see [Section 8.7](#)).
- Two sequential absolute neutrophil counts $<1.0 \times 10^9/L$ ($<1000/mm^3$).
- Two sequential hemoglobin values <8.0 g/dL (80 g/L) or decreases of $>30\%$ from baseline value.
- Two sequential platelet counts $<75 \times 10^9/L$ ($<75,000/mm^3$).
- Two sequential absolute lymphocyte counts $<0.5 \times 10^9/L$ ($<500/mm^3$).
- Two sequential AST or ALT elevations ≥ 3 times the upper limit of normal with at least one total bilirubin value ≥ 2 times the upper limit of normal.^a
- Two sequential AST or ALT elevations ≥ 3 times the upper limit of normal accompanied by signs or symptoms consistent with hepatic injury (eg, new onset elevated PT/INR).^a
- Two sequential AST or ALT elevations >5 times the upper limit of normal, regardless of total bilirubin or accompanying signs or symptoms.^a
- Two sequential increases in serum creatinine $>50\%$ AND an absolute increase in serum creatinine >0.5 mg/dL (44 $\mu\text{mol/l}$) over the average of screening and baseline values.
- Two sequential creatine kinase (CK) elevations >10 times the upper limit of normal, unless the causality is known not to be medically serious (eg, exercise or trauma induced).
- A confirmed positive urine pregnancy test in a woman of childbearing potential.
- Any opportunistic infections considered significant by the investigator or the Sponsor.
- Other serious or severe adverse events, in the opinion of the investigator or Sponsor. Whenever possible, the investigator should consult with a member of the Pfizer study team before discontinuation of the subject.

^a In each case, there is a need for additional investigations, such as review of ethanol, recreational drug and dietary supplement consumption; testing for acute hepatitis A, B or C infection and biliary tract imaging should be promptly discussed with the Sponsor or designee.

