7.6.9.2. Discontinuation Criteria

Both study drugs (Tofacitinib and MTX or placebo) will be discontinued and the subject withdrawn from the sub-study in the event of any of the following:

- Requirement of rescue medications for more than 10 consecutive days.
- Serious infections, defined as any infection (viral, bacterial, or fungal) requiring parenteral antimicrobial therapy or hospitalization for treatment, or meeting other criteria that require the infection to be classified as a serious adverse event (see [Section 8.7](#) of the LTE study).
- Two sequential absolute neutrophil counts $<1.0 \times 10^9$ cells/L (<1000 cells/mm³).
- Two sequential absolute lymphocyte counts $<0.5 \times 10^9$ cells/L (<500 cells/mm³).
- Two sequential hemoglobin values <8.0 g/dL (80 g/L) or decreases of $>30\%$ from baseline value (Day 1 of the sub-study).
- Two sequential platelet counts $<75 \times 10^9$ cells/L ($<75,000$ cells/mm³).
- Two sequential AST or ALT elevations ≥ 3 times the upper limit of normal with at least one total bilirubin value ≥ 2 times the upper limit of normal.^a
- Two sequential AST or ALT elevations ≥ 3 times the upper limit of normal accompanied by signs or symptoms consistent with hepatic injury (eg, new onset elevated PT/INR).^a
- Two sequential AST or ALT elevations >5 times the upper limit of normal, regardless of total bilirubin or accompanying signs or symptoms.^a
- Two sequential increases in serum creatinine $>50\%$ AND an absolute increase in serum creatinine >0.5 mg/dL (44 μ mol/l) over the baseline value (Day 1) in the sub-study.
- Two sequential creatine kinase (CK) elevations >10 times the upper limit of normal, unless the causality is known not to be medically serious (eg, exercise or trauma induced).
- A confirmed positive urine pregnancy test in a woman of childbearing potential.
- Any opportunistic infection considered significant by investigator or Sponsor.

- Other serious or severe adverse events, in the opinion of the investigator or Sponsor. Whenever possible, the investigator should consult with a member of the Pfizer study team before discontinuation of the subject.

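### Sub-study Section 5.9.1 allows a temporary pause for serious infections, but the sub-study stopping rule requires withdrawal for the same event

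*Protocol*

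**What the plan says.** **The pause rule.** Appendix 10 Section 5.9.1 has two tiers of interruption.

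- For a non-serious infection or other medical condition, "temporary withholding is permitted for up to 5 days of tofacitinib and 1 weekly dose of MTX". A longer break for a medical reason needs approval from the sponsor's clinician.
- A second paragraph allows tofacitinib and/or MTX to be paused for at most 14 days in a row, or two weekly doses. Its listed reasons include severe cytopenias, surgery and other moderately severe adverse events. The infection reason reads "for infections which meet criteria for serious infections (ie, those requiring parenteral antimicrobial therapy or hospitalization").

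The section closes by sending the reader to Appendix 4.3 for withdrawal on safety grounds.

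**The stopping rule.** Appendix 10 Section 7.6.9.2 says "Both study drugs (Tofacitinib and MTX or placebo) will be discontinued and the subject withdrawn from the sub-study" for any event on its list. That list includes "Serious infections, defined as any infection (viral, bacterial, or fungal) requiring parenteral antimicrobial therapy or hospitalization for treatment", and also infections that are serious adverse events on other grounds. Appendix 4.3 has the same entry: "Serious infections, defined as any infection (viral, bacterial, and fungal) requiring parenteral antimicrobial therapy or hospitalization for treatment". Section 8.6.1, which Appendix 10 Section 8 applies to the sub-study, says: "A subject who experiences a serious infection should be discontinued from the study".

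**The main extension study.** Section 5.8 allows its pause "for infections which do not meet criteria for serious infections (ie, those requiring parenteral antimicrobial therapy or hospitalization"). Appendix 4.2 allows it "for infections which do not meet criteria for serious infections (those requiring parenteral antimicrobial therapy or hospitalization").

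**The concern.** The same clinical event leads to two incompatible instructions. A time-limited temporary discontinuation implies that dosing resumes. Withdrawal means it does not. A site that follows Section 5.9.1 could restart an immunosuppressant after an infection that needed hospital care or parenteral treatment, and it would not know whether the subject was also restarting active MTX.

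The protocol's own standards show that this matters. Section 1.2.4.2 opens its account of tofacitinib's risks with serious and other important infections. It adds that serious infections were more frequent in subjects previously treated with biologics, and one of the two qualifying studies, A3921125, enrolled inadequate responders to TNF inhibitors. Sub-study exclusion criterion 14 bars entry after an infection of this severity in the preceding 3 months, yet Section 5.9.1 would allow re-dosing within 14 days of one. Safety and tolerability are the sub-study's secondary objective.

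**Working it through.** **Step 1: compare trigger and action.**

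| Place | Infection trigger | Action |
|---|---|---|
| Appendix 10, 5.9.1 (second tier) | Meets serious-infection criteria (parenteral antimicrobials or hospitalization) | Pause, at most 14 days or 2 weekly doses |
| Appendix 10, 7.6.9.2 | Same two criteria, plus infections that are serious on other grounds | Stop both drugs and withdraw |
| Appendix 4.3 | As 7.6.9.2 | Stop drug and withdraw |
| 8.6.1 (via Appendix 10 Section 8) | As 7.6.9.2 | Subject should be discontinued |
| 5.8 and Appendix 4.2 (main study) | Does **not** meet the criteria | Pause, at most 28 days |

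Every infection covered by the 5.9.1 clause is also covered by 7.6.9.2, so the conflict arises each time the clause is used.

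**Step 2: can the reader repair it?** The 5.9.1 sentence closely follows the one in Section 5.8 without the negation, so a dropped *do not* is the likely cause. That is an inference. A site reading 5.9.1 sees a 5-day tier for non-serious infections followed by a longer tier for serious ones, which can look deliberate. Appendix 10 Section 6.3 adds to that impression: it withdraws subjects whose interruption exceeds 14 days, so a shorter one looks compatible with staying in.

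**Step 3: how often could it arise?** The plan gives no figure to reproduce, and the conflict does not depend on one. The inputs are 180 subjects (Appendix 10 Section 3) and 12 months of 28 days. The infection rates and the 20% dropout are assumptions.

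- Exposure if all complete: 180 × (12 × 28) / 365.25 = 165.6 patient-years.
- With 20% dropout spread evenly over the period: 165.6 × 0.9 = 149.0 patient-years.
- Expected events = patient-years × rate / 100.
- Chance of at least one = 1 − exp(−expected events).

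| Assumed rate per 100 patient-years | Expected events, all complete | Chance of at least one | Expected events, 20% dropout | Chance of at least one |
|---|---|---|---|---|
| 0.5 | 0.83 | 56% | 0.75 | 53% |
| 1 | 1.66 | 81% | 1.49 | 78% |
| 2 | 3.31 | 96% | 2.98 | 95% |
| 3 | 4.97 | 99% | 4.47 | 99% |

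The chance passes 50% when the rate exceeds ln 2 / 1.656 = 0.42 per 100 patient-years, or ln 2 / 1.490 = 0.47 with the dropout. At 0.2 or 0.3 per 100 patient-years with all completing, it is 1 − exp(−0.331) = 28% or 1 − exp(−0.497) = 39%.

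**The case against.** The best defence is that the withdrawal rule dominates. Section 5.9.1 only permits a pause, whereas 7.6.9.2 and Appendix 4.3 are mandatory, and 5.9.1 itself ends with the pointer to Appendix 4.3. Unsupervised re-dosing is also less likely than the bare text suggests. Interruptions beyond 5 days, or beyond one weekly MTX dose, need sponsor approval. An infection needing hospital admission is a serious adverse event, which must be reported to the sponsor within 24 hours.

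These points reduce the risk but leave the permission in place. A first pause of 5 days or less needs no prior approval. The approval step covers longer interruptions and does not tell anyone that a serious infection means withdrawal. Outpatient parenteral treatment is not automatically a serious adverse event under Section 8.7, so prompt reporting may not catch it. The closing pointer puts the contradiction inside 5.9.1 itself.

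The objection to the event counts is fair. Rates below 0.5 cannot be ruled out: subjects have completed at least 24 months on tofacitinib under a rule that withdraws anyone with a serious infection, and recent infections of this severity are excluded. Falling under both rules is also not the same as being re-dosed. The counts indicate scale only.

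**Conclusion.** The concern holds. Section 5.9.1 of Appendix 10 is wrong as written: it permits a pause for an event that 7.6.9.2 and Appendix 4.3 say must end participation. This follows from the text alone.

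Its size depends on an unknown rate. Across assumed rates of 0.5 to 3 per 100 patient-years, about 0.8 to 5.0 subjects would meet both rules if all 180 enrol and complete. A better-than-even chance of at least one requires a rate above about 0.42. With so few expected events, the effect on the Month 6 HAQ-DI and PASDAS estimates is likely to be small. It should be corrected because it is a patient-safety instruction that contradicts the stopping rule.

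**What to change.** In Appendix 10 Section 5.9.1, delete the serious-infection clause from the reasons for the 14-day or two-dose pause, and add: *Serious infections are governed by Section 7.6.9.2 and Appendix 4.3: both study drugs are discontinued and the subject is withdrawn.* Non-serious infections then stay under the existing 5-day, one-dose tier, which can be extended with sponsor approval.

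Restoring the negation, as in Section 5.8, would also work. It would create a 14-day tier for non-serious infections that overlaps the 5-day tier, so the text would have to say how the two limits relate. Deletion is cleaner.

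The cost is a few words in a protocol amendment or administrative letter, with no extra visits or subjects.
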